**Date: 2023-01-16**

## Research Plan

### Background and Research Question

Epidemiological studies show that regular physical activity reduces the risk of developing several types of cancer (2,7). Furthermore, it has been suggested that physical activity can prevent tumor growth, as multiple studies indicate a reduced risk of recurrence in physically active cancer patients (1). These studies are observational and do not explain how physical activity reduces the risk of developing cancer. One proposed mechanism is the impact of physical activity on the immune system (3). Physical activity mobilizes leukocytes into the bloodstream and changes the levels of hormones and various metabolites in the blood, such as catecholamines, lactate, and intermediates in the TCA cycle (13,14). The latter is interesting because metabolism and metabolites in the local environment are directly linked to the activation and development of leukocytes (8,9).

The immune system inhibits cancer through continuous immunological surveillance, where different cells in the immune system identify and destroy malignant cells. High levels of CD8 T-cells, CD45RO+ T-memory cells, and NK cells in a tumor are linked to better prognoses for several cancers, while high levels of regulatory T-cells and myeloid cells are associated with tumor progression (4,12). CD8 T-cells prevent tumor growth by binding tumor-associated antigens, becoming activated effector cells, and eliminating cancer cells with their cytotoxic granules. The principal investigator recently published a study on a breast cancer model in mice, where exercising mice had slower cancer growth and lived longer than non-exercising mice (11). This effect was mediated by CD8 T-cells, which were activated and gained greater cytotoxic capacity from metabolites secreted into the bloodstream and secondary lymphoid organs during physical activity. Furthermore, lactate injections inhibited tumor growth in the mice, and lactate increased CD8 T-cell expansion in vitro. This is highly interesting because intense exercise can increase blood lactate levels more than tenfold from resting values (5). Thus, this study presents a potential mechanism by which physical activity can prevent tumor growth by potentiating the anti-tumor effects of CD8 T-cells and suggests a role for lactate in this process. Metabolites influence T-cell activation (10), and metabolic changes in activated T-cells are linked to epigenetic modifications such as histone and DNA acetylation and methylation (6). Whether epigenetic modifications also occur in T-cells after physical activity is crucial to study, as several metabolites are elevated both locally within tumors and in working muscles and blood after a workout.

The overarching question for this project is whether physical activity can alter the anti-tumor properties of T-cells. The goal is to study the functional effects of different types of exercise on T-cells, focusing on metabolism, epigenetic modification, activation, and functions related to cytotoxic properties.

### Method

To describe how the immune system, specifically T-cells, reacts to exercise, we use high-intensity interval training: a high-intensity session consisting of three 30-second maximal cycling efforts with resistance equivalent to 7.5% of body weight. Training sessions and venous blood sampling, including blood lactate measurement, will be conducted in an existing research facility at the Division of Clinical Physiology.

**Flow Cytometry:** Immune cells will be analyzed using a flow cytometer at CIM, KI. Different antibody panels will be used to characterize the phenotype of leukocytes, particularly CD8 T-

cells, by using functional markers such as CD45RA, PD-1, CCR7, CTLA-4, Granzyme-B, CD62L, and ICOS.

**Cell Culture:** PBMCs will be isolated from blood using CPT tubes, and T-cells will be isolated via magnetic sorting and cultured in the presence of IL2 and CD3/CD28 Dynabeads to activate and proliferate them. To test the effect of intracellular lactate on T-cells, Rotenone (which increases lactate) or Dichloroacetate (which decreases lactate) will be added. To study the effect of extracellular lactate, sodium lactate will be added. Expansion and viability will be measured before and after each experiment, and flow cytometry will be conducted before and after culture.

**Cytotoxicity:** CD8 T-cells will be frozen after isolation and used within six months to examine the production of effector molecules in a 96-well plate, known as Elispot. Frozen CD8 T-cells will also be cultured with a cancer cell line to observe whether the CD8 T-cells affect the viability of cancer cells.

**Cell Metabolism:** Characterization of T-cell metabolism before and after physical activity will be performed using Seahorse. RNA-seq will analyze gene expression in CD8 cells after exercise. ATAC-seq will analyze accessible chromatin, which will be sequenced and mapped to genes and possible transcription factors. Samples will be sent to SciLife lab, Solna, for ATAC-seq and bioinformatic analysis.

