### **Work Plan Including Preliminary Data**

We have preliminary data showing that a high-intensity exercise session in humans leads to a threefold increase in CD8 T-cells and a twofold increase in CD4 T-cells in the blood, and blood lactate levels increase from about 1 mmol/L at rest to almost 20 mmol/L after high-intensity exercise (n=3). Preliminary data from SeaHorse show that CD8 T-cells taken after physical activity reduce their glucose metabolism compared to CD8 T-cells taken before physical activity.

**Study Plan:** Young, healthy subjects (n=20, men and women) will perform a high-intensity exercise session consisting of three 30-second maximal cycling efforts, which constitutes significant metabolic stress and results in high blood lactate levels. Venous blood samples will be taken before, immediately after, and 60 minutes after exercise and analyzed by flow cytometry, focusing on T-cell characterization. A venous blood gas will be taken before, immediately after, 30 minutes after, and 60 minutes after exercise. T-cells will be isolated from blood and cultured in the cell lab. Cell count and viability will be measured after culture to study the effect of a preceding high-intensity exercise session on T-cell expansion. Since T-cell metabolism affects their function, Seahorse will be used to study the metabolism of CD8 T-cells isolated in connection with high-intensity exercise. Cytotoxicity will be measured by culture with cancer cell lines and by cytokine secretion upon activation. RNA-seq will be performed on CD8 T-cells isolated before and immediately after exercise.

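### Rotenone and dichloroacetate cannot by themselves attribute a T-cell effect to intracellular lactate, and no sodium-matched comparator is specified for the sodium lactate cultures

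*Protocol*

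**What the plan says.** The Cell Culture paragraph of the Protocol's Method section describes two ways of manipulating lactate in isolated, activated T-cells. For lactate inside the cell: "To test the effect of intracellular lactate on T-cells, Rotenone (which increases lactate) or Dichloroacetate (which decreases lactate) will be added". For lactate outside it: "To study the effect of extracellular lactate, sodium lactate will be added". The readouts follow in the next sentence: "Expansion and viability will be measured before and after each experiment, and flow cytometry will be conducted before and after culture".

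The reason for asking is in Background and Research Question, where the earlier mouse work "suggests a role for lactate in this process". The only lactate concentrations in either document are preliminary blood values from three people, in Work Plan Including Preliminary Data: "blood lactate levels increase from about 1 mmol/L at rest to almost 20 mmol/L after high-intensity exercise".

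Neither document gives a concentration for rotenone, dichloroacetate or sodium lactate, names an untreated, vehicle or sodium-matched comparator, or plans a lactate measurement in the treated cultures. The Study Plan does not return to these three agents, and the SAP has no factor or contrast for them.

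**The concern.** The stated purpose of the drug cultures is to learn what intracellular lactate does to T-cells. That inference needs a manipulation that changes lactate and leaves other determinants of expansion and viability alone, or a design that lets the two be told apart. Neither is described. The sodium lactate cultures have a similar but more easily cured problem: each lactate ion arrives with a sodium ion, so a comparison with plain medium changes sodium and osmolality along with lactate.

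What is at stake is the mechanistic statement about lactate. The exercise session cannot supply it, because the Protocol says that catecholamines and other metabolites also change with exercise. The cultures are the only part of the plan that manipulates lactate directly, so their comparators decide whether anything can be said about lactate as such.

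**Working it through.** The plan states no figure that could be reproduced here. The check is a reading of the passages together, a sign argument for the drug cultures, and one illustrative calculation for sodium lactate.

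**Step 1. Is there a second route from the drugs to the readouts?** The Protocol describes each agent only by the direction in which it moves lactate. That rotenone raises lactate by blocking mitochondrial respiration, and that dichloroacetate lowers it by diverting pyruvate into oxidation, is general pharmacology that the documents do not give; I take it as an assumption. The Study Plan supplies the other half: "Since T-cell metabolism affects their function, Seahorse will be used to study the metabolism of CD8 T-cells isolated in connection with high-intensity exercise". If metabolism affects function, an agent that alters metabolism can change expansion or viability without lactate being the cause.

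**Step 2. Does using two opposing drugs separate the routes?** Write the effect of an agent on expansion as

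effect = a × (change in lactate) + b × (change in respiration).

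Under the assumption in Step 1 the changes have these signs:

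- rotenone: lactate up, respiration down;
- dichloroacetate: lactate down, respiration up.

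Compare the two simple explanations:

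- lactate alone matters and promotes expansion (a > 0, b = 0): rotenone increases expansion, dichloroacetate decreases it;
- respiration alone matters and restrains expansion (a = 0, b < 0): rotenone increases expansion, dichloroacetate decreases it.

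The predicted patterns are the same. Reversing both signs (a < 0, b = 0 against a = 0, b > 0) again gives one shared pattern, with rotenone decreasing and dichloroacetate increasing expansion. Opposite drug effects therefore fit either explanation. A lactate reading in these cultures would confirm that lactate moved as intended, but would not break the link.

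**Step 3. How much do sodium and osmolality move in the sodium lactate cultures?** Inputs: concentration c, not stated, illustrated with the blood range of about 1 to almost 20 mmol/L; full dissociation, assumed; medium osmolality of 290 mOsm/L, assumed.

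Added sodium = c. Added osmolality = 2c (one sodium plus one lactate). Relative increase = 2c / 290.

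- c = 1 mmol/L: 2 mOsm/L; 2/290 = 0.7%
- c = 10 mmol/L: 20 mOsm/L; 20/290 = 6.9%
- c = 20 mmol/L: 40 mOsm/L; 40/290 = 13.8%

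At the low end the change is negligible. At concentrations meant to mimic intense exercise it is not, unless the comparator carries the same sodium load. Equimolar sodium chloride adds the same c of sodium and the same 2c of osmolality, so both cancel in the contrast.

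**The case against.** The strongest reply is that the Cell Culture paragraph is a short summary. It also omits concentrations, vehicle and untreated wells, and a competent laboratory may run all of these. This stands as far as it goes: the documents support saying that no matched comparator is specified, not that none will be used. Nor does the Protocol say that the drugs change only lactate; it simply mentions no other action.

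A second reply is that the plan already triangulates, with one agent raising lactate, one lowering it, and a separate arm adding lactate itself. That deserves credit, and the sodium lactate arm does offer a route that does not depend on altering respiration. But the two drugs do not isolate lactate between them, and the third arm helps only against a matched comparator.

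Third, the mechanism assumed for the drugs comes from outside the documents, and the sentence on metabolism and function introduces the Seahorse work on cells taken around exercise, not the drug cultures. This is correct. The sentence supports the general premise; the mechanism remains an assumption, though a basic one.

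Fourth, the lactate cultures are ancillary. The overarching question and goal in the Background concern exercise and T-cells and do not name lactate. This also stands and limits the point's weight.

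A reader might infer more: that a fall in expansion under rotenone would be reported as lactate inhibiting T-cells, reversing the mouse study's finding that lactate increased CD8 T-cell expansion in vitro. The documents contain no rule for interpreting these cultures, so that reading, and the sign reversal built on it, is conjecture.

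**Conclusion.** The point holds within a narrow scope. As described, the rotenone and dichloroacetate cultures alone cannot attribute an effect to intracellular lactate, and the sodium lactate cultures lack a specified comparator that would remove sodium and osmolality as explanations.

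The confounding with mitochondrial metabolism cannot be sized from the documents. The osmolality figure is illustrative: about 14% at 20 mmol/L and 7% at 10 mmol/L, given full dissociation and a 290 mOsm/L medium. The 20 mmol/L is a blood value rather than a planned culture concentration, and nothing in the documents shows that a shift of this size changes T-cell expansion.

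The pre/post-exercise comparisons (flow cytometry, Seahorse, RNA-seq, cytotoxicity) are unaffected. It would be wrong to infer that the project's main question is compromised, because the exercise comparisons do not rely on these cultures.

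**What to change.** In the Cell Culture paragraph of the Method section:

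1. Compare each sodium lactate concentration with equimolar sodium chloride wells from the same donor, and base any conclusion about extracellular lactate on that within-donor contrast alone.
2. Measure lactate in the rotenone and dichloroacetate cultures, to confirm that it moved as intended.
3. Report the rotenone and dichloroacetate results as effects of the agent, or of altered mitochondrial metabolism, not of intracellular lactate.

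Agreement of the drug arms should not be a condition for accepting a sodium lactate effect. Such a rule would let the confounded arms overturn a properly controlled contrast, and would merge the intracellular and extracellular questions that the Protocol keeps apart.

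The cost is a few more wells and cells per donor and some lactate readings, with no extra subjects or blood draws. If the cultures are already complete, the third item still applies and costs nothing.

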### **Work Plan Including Preliminary Data**

We have preliminary data showing that a high-intensity exercise session in humans leads to a threefold increase in CD8 T-cells and a twofold increase in CD4 T-cells in the blood, and blood lactate levels increase from about 1 mmol/L at rest to almost 20 mmol/L after high-intensity exercise (n=3). Preliminary data from SeaHorse show that CD8 T-cells taken after physical activity reduce their glucose metabolism compared to CD8 T-cells taken before physical activity.

**Study Plan:** Young, healthy subjects (n=20, men and women) will perform a high-intensity exercise session consisting of three 30-second maximal cycling efforts, which constitutes significant metabolic stress and results in high blood lactate levels. Venous blood samples will be taken before, immediately after, and 60 minutes after exercise and analyzed by flow cytometry, focusing on T-cell characterization. A venous blood gas will be taken before, immediately after, 30 minutes after, and 60 minutes after exercise. T-cells will be isolated from blood and cultured in the cell lab. Cell count and viability will be measured after culture to study the effect of a preceding high-intensity exercise session on T-cell expansion. Since T-cell metabolism affects their function, Seahorse will be used to study the metabolism of CD8 T-cells isolated in connection with high-intensity exercise. Cytotoxicity will be measured by culture with cancer cell lines and by cytokine secretion upon activation. RNA-seq will be performed on CD8 T-cells isolated before and immediately after exercise.

### **Significance**

With this project, we aim to increase understanding of the mechanism by which physical activity can inhibit tumor growth. Active CD8 T-cells and ongoing immunological surveillance have a strong connection to prognosis, and in the proposed project, we want to study how different exercise modalities affect the number and function of circulating T-cells. These different modalities vary in duration and intensity, involving different stress levels, such as varying

catecholamine levels and exercise-induced metabolites like lactate. The strength of this project lies in studying cytotoxic T-cells within the same population, exposed to different types of exercise, and using relevant methods to examine expansion, metabolism, and expression of functional markers. By studying the effect of different exercise modalities, we hope to obtain information on what aspects of exercise are beneficial, which in turn can support the formulation of recommendations for affected individuals and the general public.

Project title:

Effekten av högintensiv träning på vita blodkroppar, med speciellt fokus på funktion kopplad till att bekämpa cancerceller.

Date: 18th of June 2024

SAP – statistical analysis plan

In general, statistical analysis is performed using GraphPad Prism version 10.1.12 (324). The statistical analysis of the RNAseq data was performed by the core facility BEA at Karolinska Institutet. In brief, Fastq-files were aligned to GRCh38 using STAR. Gene counts were processed using DESeq2 and the Wald test, with the apeglm method for log fold change shrinkage. The design was ~individual+condition (pre- or post-exercise). Benjamini & Hochberg was employed to adjust for multiple testing. Gene set enrichment analysis was performed using the fgsea package and the function fsgseaMultilevel in R version 4.1.2 to compare the signature of genes in CD8+ cells post and pre-exercise versus the GO signatures from the Molecular Signatures Database.

For the blood gas data and the absolute cell number data, one-way RM ANOVA with Tukey´s multiple comparisons test was utilized. For analysis of flow cytometry data, paired t-test was used both for pre/post comparison of individual surface marker expressions and for the cluster analysis. For metabolism assays using SeaHorse, RM two-way ANOVA with Sídáks multiple comparison test and paired t-test was used. For the analysis of IFN-gamma expression, paired t-test was used. For the cytotoxicity data, RM two-way ANOVA with Sídáks multiple comparison test was used.

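### Absolute cell counts are compared across a maximal sprint session with no stated correction for haemoconcentration, so any fluid shift is included in the apparent rise in circulating T-cells

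*SAP*

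**What the plan says.** The only analysis text for this endpoint is in the SAP: "For the blood gas data and the absolute cell number data, one-way RM ANOVA with Tukey´s multiple comparisons test was utilized". It names no unit, derivation, normalisation or covariate for the absolute cell number.

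The protocol's Method section describes the stimulus as "three 30-second maximal cycling efforts with resistance equivalent to 7.5% of body weight". Under Work Plan Including Preliminary Data, the cell samples are set out thus: "Venous blood samples will be taken before, immediately after, and 60 minutes after exercise and analyzed by flow cytometry". The blood-gas schedule follows: "A venous blood gas will be taken before, immediately after, 30 minutes after, and 60 minutes after exercise". A blood gas is therefore drawn at all three cell-sampling times, but the variables to be recorded from it are not listed.

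The same section reports preliminary data (n=3) in which a session "leads to a threefold increase in CD8 T-cells and a twofold increase in CD4 T-cells in the blood". The Background says "Physical activity mobilizes leukocytes into the bloodstream", and the Significance section says "we want to study how different exercise modalities affect the number and function of circulating T-cells".

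**The concern.** A venous sample gives cells per volume unless blood volume is also measured, and no such measurement is planned. If plasma water leaves the circulation during maximal effort, every cell type becomes more concentrated whether or not any cell has entered the blood. The contrast between rest and immediately after exercise then combines release of cells with loss of fluid, and nothing in the plan separates them.

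The shift is expected to run the same way in every subject. It is a bias and not noise, so the within-subject design and the 20 subjects leave it in place; more precision only makes it easier to declare significant. Three results are exposed: the size of the fold changes, any subset whose count changes little, and the comparison of 60 minutes with rest if blood volume has not recovered by then.

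**Working it through.** **Inputs from the documents.** n=20, one group, three cell-sampling times, RM ANOVA with Tukey comparisons; preliminary ratios of 3 (CD8) and 2 (CD4), from n=3, with no SD. The plan states no power, SD or fluid shift, so it has no figure to reproduce.

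**Assumptions.** Counts are per volume of blood. Haemoglobin rises by h = 5%, 10% or 15% immediately after exercise. The SD of the log post/pre ratio is 0.15, 0.20 or 0.30. Counts are analysed on the log scale, which the SAP does not specify.

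**Step 1: effect on the fold changes.** If the mass of circulating haemoglobin is constant, corrected ratio = observed ratio / (1 + h). The share of the observed rise due to fluid is (observed − corrected) / (observed − 1).

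| h | CD8, observed 3 | Fluid share | CD4, observed 2 | Fluid share |
|---|---|---|---|---|
| 5% | 3/1.05 = 2.86 | 0.14/2 = 7% | 2/1.05 = 1.90 | 0.095/1 = 10% |
| 10% | 3/1.10 = 2.73 | 0.27/2 = 14% | 2/1.10 = 1.82 | 0.18/1 = 18% |
| 15% | 3/1.15 = 2.61 | 0.39/2 = 20% | 2/1.15 = 1.74 | 0.26/1 = 26% |

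For a small observed ratio of 1.2, the corrected values are 1.14, 1.09 and 1.04, so fluid would account for 29%, 55% or 78% of the rise.

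**Step 2: is the range plausible?** With resting haematocrit Hct and fractional plasma loss p, the blood-volume ratio is Hct + (1 − Hct)(1 − p), and the spurious rise is 1/ratio − 1. Taking Hct 0.40 to 0.45 and p from 5% to 20% (also assumptions), the ratio runs from 0.9725 to 0.88 and the spurious rise from 2.8% to 13.6%. In reverse, h = 10% needs p = (1 − 1/1.10)/(1 − Hct), about 15% to 17%, and h = 15% needs about 22% to 24%. The 15% case therefore lies just beyond this range.

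**Step 3: false calls when no cell is mobilised.** The Tukey critical value for three times and 38 df, on the t scale, is 2.439. The standard error of the mean log ratio is SD/√20, and the noncentrality is log(1 + h)/(SD/√20). For h = 10% and SD 0.20 this is 0.0953/0.0447 = 2.13. The probability of declaring a rise, from the noncentral t, is:

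| h | SD 0.15 | SD 0.20 | SD 0.30 |
|---|---|---|---|
| 5% | 18% | 10% | 5% |
| 10% | 66% | 39% | 17% |
| 15% | 95% | 75% | 37% |

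With no fluid shift the corresponding probability is about 1%.

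**The case against.** The strongest reply is that the SAP names tests and does not describe how the data are derived. It gives no unit for the absolute cell number and does not use the word concentration, so it cannot be read as stating that uncorrected concentrations are tested. That stands: the text shows only that no correction is stated.

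A reader might also infer that the plan counts fluid shift as T-cell mobilisation. The documents do not support this. The preliminary result is worded as an increase in the blood, mobilisation appears only as general background, and no planned analysis claims net release of cells. Cells per volume is a legitimate description of circulating blood. It misleads only if it is read as release, although the background makes that reading a natural one.

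The size is also open to challenge. No fluid shift or SD is given, the high false-call rates need a subset with no mobilisation at all, and at a 5% shift they fall to between 5% and 18%. Sampling uncertainty in ratios from three subjects may well exceed the correction. All of this limits the weight of the point, but it does not remove a one-directional error from the planned contrast.

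Finally, the scope is narrow. Within-sample percentages, marker expression and assays on isolated cells (Seahorse, cytotoxicity, IFN-gamma, RNA-seq) are not directly affected by concentration.

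**Conclusion.** The concern holds for absolute cell numbers, provided they are counts per volume. Under an assumed 5 to 15% haemoglobin rise, fluid accounts for roughly 7 to 20% of a threefold CD8 rise and 10 to 26% of a twofold CD4 rise. It would be wrong to infer that haemoconcentration explains the preliminary increases: both survive correction across the whole assumed range.

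The practical exposure is in overstated fold changes and in subsets with small changes, where a rise could be declared with no mobilisation behind it. How often depends heavily on a shift and an SD that the documents do not give. The 60-minute contrast is affected only if blood volume has not returned to its resting value, which the documents do not address. This is worth correcting because it is systematic and cheap to deal with; it does not threaten the study's main reading.

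**What to change.** State the unit of absolute cell number in the SAP, and state whether the blood gas reports haemoglobin or haematocrit.

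If it does, multiply each post-exercise count by Hb(rest)/Hb(time), or by the matching haematocrit ratio. Repeat the RM ANOVA with Tukey comparisons on the corrected counts and report them beside the uncorrected ones. Base any claim of net mobilisation on the corrected counts.

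If neither was recorded, word the conclusions as changes in cell concentration and do not describe them as mobilisation.

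The cost is a sentence or two in the SAP and one multiplication per post-exercise sample, with no extra blood draw if the values are already on the blood-gas record. The downside is slightly smaller fold changes and a little measurement noise added by the haemoglobin or haematocrit reading.
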